- For evaluable patients who previously withdrew from treatment, they will be imputed as a non-responder until their maximum hypothetical visit (i.e., the maximum visit that they could have attended if they had remained within the program).
 - For visits after a patient's maximum hypothetical evaluable visit, they will be removed from the analysis.

Maximum Hypothetical Evaluable Visit

A patient's maximum hypothetical study day (i.e., the maximum visit that they could have attended if they had remained within the study) is calculated as follows:

Maximum hypothetical study day = (15th May 2022 - Patient's Day 1 OLE enrollment date)

For the hybrid LOCF analysis and non-responder analyses, this will impute patients who have withdrawn as a non-responder until the 15th May 2022, which was the latest day of dosing reported in the closure of the study announcement. This excludes patients who withdrew from study drug with reason being stated as "study terminated by sponsor" after 15th February 2022, these patients will not be imputed as non-responders and will be considered 'treatment completers' for the efficacy analysis with data included "as observed".

Simple Endoscopic Score for Crohn's disease (SES-CD) score: Handling of Partially Available Segments

Note that in the OLE study GA29145, no central adjudication took place and therefore only a local score will be available for the Week 108 assessment. This differs from Study GA29144, which utilized central adjudication and up to 3 readers provided a score. To overcome differences in reader availability between studies the following approach will be used:

Baseline score will utilize data from all available readers with adjudication applied to determine the final total SES-CD score. This aligns with the original Day 1 Baseline score in study GA29144 and ensures that the central readers are retained in the Baseline score derivation, as reported in the CSR analysis.

The determination of segment availability will use the Local reader only for both the baseline and post-baseline time points, as follows:

- any segment(s) missing by the local reader at baseline will not be considered in the Week 108 visit total SES-CD total score calculation

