- any segments(s) available at baseline that are not available at Week 108 will result in a non-responder status for the patient for endoscopic improvement/remission. For continuous data the patient's baseline segment score will be carried forward (BOCF) to impute the Week 104 segment score when calculating the total SES-CD score.

4.1.3.1 Endoscopic Improvement and Remission at Week 108

As endoscopy data is only collected at a common time point of Week 108 during the OLE Study GA29145, the endpoints of endoscopic improvement and endoscopic remission will be summarized only at this time point. These endpoints will be examined overall and separated by their previous endoscopic improvement status at their latest visit prior to enrollment into GA29145 i.e., at the parent study's (GA29144) Week 14 or Week 66.

The handling of patients with partially available segments is detailed in Section [4.1.3](#), this is not considered as true missing data.

Population: All patients who enrolled into Part 1 of the OLE Study GA29145.

Baseline: The original baseline value from the parent study will be used to calculate improvement.

Sub-groups:

- All patients overall and split by prior endoscopic improvement status and their prior aTNF exposure status.

Analysis 1 - Non-Responder

Missing data: Patients who are non-evaluable at Week 108 (i.e., could not have reached the maximum visit if they had remained within the program as detailed in Section 4.1.3) will be removed from the analysis. Patients who remain in Study GA29145 but are missing endoscopy scores (i.e., the assessment was not done) will be imputed as non-responders within the analysis, as LOCF is not appropriate when endoscopy data is not collected routinely.

Intercurrent events: Patients who withdraw during Study GA29145 will be set to non-responders using the composite strategy if they could have reached OLE Week 108 at the time of the clinical cut-off date had they not withdrawn from treatment. This excludes patients who withdrew from study drug on or after 15th February 2022.

Analysis 2 - As Observed

Missing data: If a patient has missing data at a visit, they will be removed from the analysis and no imputation will be performed.

Intercurrent events: No imputation will be performed for treatment withdrawals

4.1.3.2 Simple Endoscopic Score for Crohn's disease (SES-CD) score at Week 108

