As endoscopy data is only collected at a common time point of Week 108 during the OLE Study GA21945, continuous SES-CD score will be summarized only at this time point and at parent study Baseline. The handling of patients with partially available segments is detailed in Section 4.1.3, this is not considered as true missing data.

Population: All patients who enrolled into Part 1 of the OLE Study GA29145.

Baseline: The original baseline value from the parent study will be used as the baseline SES-CD score.

Analysis 1 - BOCF

Missing data: If a patient has missing data at a visit (i.e., the assessment was not done), they will be removed from the analysis and no imputation will be performed.

Intercurrent events: No imputation will be performed for treatment withdrawals

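### A segment the local reader left unscored at baseline is dropped from the Week 108 SES-CD total but not from the baseline total, so a fall can be recorded without healing

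*SAP*

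**What the plan says.** Week 108 SES-CD is a listed efficacy outcome (SAP 1.3.1). The change from parent-study Week 0, and a threshold of 4 or less (2 or less for ileal patients) with no subscore above 1, are exploratory outcomes (SAP 1.3.3).

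In the parent study, GA29144, "up to 3 readers provided a score", with central adjudication. In the extension only the investigator scores the endoscopy. SAP 4.1.3 acknowledges this difference and sets these rules:

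- Baseline total: "Baseline score will utilize data from all available readers with adjudication applied to determine the final total SES-CD score". The stated purpose is that this "ensures that the central readers are retained in the Baseline score derivation".
- Availability: "The determination of segment availability will use the Local reader only for both the baseline and post-baseline time points".
- Segment the local reader did not score at baseline: "any segment(s) missing by the local reader at baseline will not be considered in the Week 108 visit total SES-CD total score calculation".
- Segment available at baseline but lost at Week 108: the patient is a non-responder for the binary endpoints. For continuous data the "baseline segment score will be carried forward (BOCF) to impute the Week 104 segment score" (the Week 104 there is presumably a slip for Week 108).

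The two endpoint sections repeat the choice of baseline. Section 4.1.3.1: "The original baseline value from the parent study will be used to calculate improvement". Section 4.1.3.2: "The original baseline value from the parent study will be used as the baseline SES-CD score". Both add that partially available segments do not count as truly missing data, so no other missing-data rule applies to them.

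**The concern.** The baseline and Week 108 totals may be summed over different sets of segments. The availability sentence covers both time points, but it only says how availability is judged. The one consequence given for a segment missing locally at baseline is its removal at Week 108. Nothing removes it from the baseline, and three separate statements keep the adjudicated parent-study total.

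If a central reader scored that segment and the adjudication counted it, its points disappear between baseline and Week 108 through the scoring rule alone. A reader of the study report could not tell that fall from healing, and a single-arm study has no control group in which the artefact would show.

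A second effect concerns the absolute Week 108 criterion. It makes no use of baseline, so comparability with baseline is no reason to leave out disease that was seen at Week 108. The exclusion nevertheless takes that disease out of the total being compared with 4 (or 2).

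**Working it through.** The plan gives no figure to reproduce. The check is SES-CD arithmetic on the rules as written.

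**Inputs.** Protocol Appendix 11: four items per segment, each scored 0 to 3, in five segments. The maximum per segment is 4 × 3 = 12. Reader and segment rules are from SAP 4.1.3. The documents do not give the parent study's rule for adjudicating a segment scored by one reader and not another, or the number of such patients; both are varied below.

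**Comparison with baseline.** Assume no true change, and readers who agree on every segment they both score. Let

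- S = points in the segments the local reader scored at baseline
- m = points in one segment the local reader did not score at baseline (0 to 12)
- w = share of the central points for that segment that enters the adjudicated baseline (0 to 1, unknown)

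Then, as written:

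- baseline = S + w·m
- Week 108 = S
- recorded change = S − (S + w·m) = −w·m

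The change is 0 if w = 0, reaches −12 for one segment if w = 1 and m = 12, and is never positive. With both totals over the same segments it is S − S = 0 for every w and m.

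Illustrations (segment scores are assumptions):

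| Segment scores (the one unscored locally is listed first) | w | Baseline | Week 108 | Recorded change | Matched segments |
|---|---|---|---|---|---|
| 4, 4, 4, 4, 4 | 0 | 16 | 16 | 0 | 0 |
| 4, 4, 4, 4, 4 | 1/2 | 18 | 16 | −2 (−11%) | 0 |
| 4, 4, 4, 4, 4 | 1 | 20 | 16 | −4 (−20%) | 0 |
| 6, 6, 0, 0, 0 | 1/2 | 9 | 6 | −3 (−33%) | 0 |
| 6, 6, 0, 0, 0 | 1 | 12 | 6 | −6 (−50%) | 0 |
| 6, 4, 0, 0, 0 | 1 | 10 | 4 | −6 (−60%) | 0 |

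**Group mean.** If a share p of patients is affected, the bias is −p·w·m. With w = 1: p = 5% and m = 4 gives −0.05 × 4 = −0.2 points; p = 20% and m = 6 gives −0.20 × 6 = −1.2 points. If p = 0 or w = 0 it is zero. These values of p are not estimates.

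**Absolute criterion.** This part does not depend on w. Take one excluded segment:

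- If the subscore clause still covers that segment, each of its four items is at most 1, so it can hold 4 × 1 = 4 points. A true Week 108 total of 4 + 4 = 8 (2 + 4 = 6 for ileal patients) could count as met.
- If the segment is excluded from the subscore clause too, the arithmetical limit is its full 12 points: 4 + 12 = 16 (2 + 12 = 14).

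The last row of the table shows the difference. Its Week 108 total of 4 meets the numerical cut, but a segment with 6 points must have an item above 1, so the patient fails if the clause covers that segment and could pass if it does not. The SAP text trims only the total and is silent on the clause.

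**The case against.** The strongest objection is that the false fall may never occur. It needs a local blank, a central score, and an adjudication rule that counted that score. If all readers judged the same procedure, a segment the endoscope did not reach would be blank for everyone and w = 0. The parent rule might also have dropped such segments already. This stands: existence and size cannot be settled from the documents, and a reader who inferred that the reported endoscopic change is inflated would be going beyond them. It does not remove the point, because the SAP brings in its rule precisely because reader availability differs between the studies, and it leaves the artefact possible.

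A second objection is that local-only availability at both time points implies a trimmed baseline. The text does not bear this out: the only stated consequence falls on Week 108, and trimming would conflict with keeping the total as reported for the parent study, unless that study had already dropped the segment.

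Third, SAP 4.1.3.2 plans summaries at Week 108 and at parent baseline and does not itself specify a change analysis. That is correct. Change is listed in SAP 1.3.3, and comparing the two summaries carries the same mismatch. Improvement has no numerical definition in the SAP, so little can be built on it.

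Fourth, the sponsor openly chose agreement with the parent report. That is a legitimate aim, and the adjudicated baseline should stay. A reader might also take the local-only Week 108 reading as the fault. It is disclosed in Protocol 4.4.4.3 and SAP 4.1.3 and is not the objection here.

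Finally, 8 and 6 might be read as firm bounds on the absolute criterion. They hold only for one excluded segment and only if the subscore clause still covers it.

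**Conclusion.** The mismatch is in the text, and its effect on the comparison with baseline is conditional. If central points for a locally unscored segment entered the adjudicated baseline, the recorded fall without healing is 0 to 12 points per segment, and through this rule the error can only favour improvement. The number of patients affected is unknown and may be nil, so no statement about the size of bias in the mean is supported.

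The omission of visible Week 108 disease from the absolute criterion needs no assumption about central readers. It needs only a patient with such a segment showing disease at Week 108. Up to 4 points per segment can be hidden if the subscore clause still applies to it, and more if it does not.

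The stakes are modest. The study has one arm, SAP 2.1 plans no testing, and SAP Section 4 limits the efficacy reported in a synoptic report. No test, alpha, power or treatment comparison is touched. The point is worth fixing because the remedy is cheap.

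**What to change.** 1. Keep the adjudicated baseline total in the baseline table and in the planned summary. Add a summary of SES-CD change for all patients, with both totals computed over the same segments: those the local reader scored at baseline. Use local-reader scores at both time points, and local baseline segment scores where the carry-forward rule applies to a segment lost at Week 108. Using one reader type throughout avoids mixing local and adjudicated baselines within one mean. If adjudicated scores exist by segment for all patients, also show the adjudicated baseline restricted to those segments.
2. For the absolute Week 108 criterion, count every segment seen at Week 108 in both the total and the subscore clause. Leave the non-responder rule for lost segments unchanged. An affected patient will then have two Week 108 totals, one for change and one for the threshold, so label them separately.
3. Report how many patients have a segment scored centrally but not locally at baseline. If there are none, the false fall described here cannot have occurred.

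The cost is some SAP wording, a small change to the threshold derivation, one extra descriptive summary and one count. The availability rule already requires the local reader's baseline record by segment. The downside is that, for affected patients, the matched baseline will differ from the total in the parent-study report; a footnote can say so.

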4.1.3 Primary Efficacy Analysis

To evaluate the efficacy of etrolizumab during long-term open-label treatment, efficacy will be summarized within the population of patients who enroll into the Study GA29145. Both endoscopic improvement and clinical remission will be summarized in two separate analyses. Due to the open-label nature of the study, no treatment comparisons will be made.

Concerning missing data and treatment withdrawal imputation, there will be 3 strategies employed, described below.

Hybrid LOCF

Within this strategy, at each visit only patients who had the possibility of reaching the visit will be considered in the analysis for that specified visit. Patients will be deemed evaluable at a visit if it was possible for them to have reached this visit based on their enrollment date and the date of the closure of Part 1 of the study.

- Patients for whom it is not possible to have reached the visit at the time of the clinical cut off are termed non-evaluable and will not be included in the analysis at that visit.
- For evaluable patients with missing data, Last Observation Carried Forward (LOCF) will be used from their most recent available data.

- For evaluable patients who previously withdrew from treatment, they will be imputed as a non-responder until their maximum hypothetical visit (i.e., the maximum visit that they could have attended if they had remained within the study).
 - For visits after a patient's maximum hypothetical evaluable visit, they will be removed from the analysis.

As Observed

Within this analysis only the available data at each visit will be summarized. No imputation will be performed for missing data or treatment withdrawals.

Non-Responder

Within this strategy, at each visit only patients who had the possibility of reaching the visit will be considered in the analysis for that specified visit. Patients will be deemed evaluable at a visit if it was possible for them to have reached this visit based on their enrollment date and the date of the closure of Part 1 of the study.

- Patients for whom it is not possible to have reached the visit at the time of the clinical cut off are termed non-evaluable and will not be included in the analysis at that visit.
- Evaluable patients with missing data will be set as a non-responder.

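### The As Observed endoscopy analysis counts a patient with one baseline-scored segment unscored at Week 108 as a failure but drops a patient with no endoscopy, so no planned binary analysis shows what the segment rule does

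*SAP*

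**What the plan says.** SAP 4.1.3, in its text on partially available SES-CD segments, decides segment availability from the local reader only. A segment that reader did not score at baseline is left out of the Week 108 total and has no further consequence. The reverse case is handled differently: "any segments(s) available at baseline that are not available at Week 108 will result in a non-responder status for the patient for endoscopic improvement/remission". For the continuous score, the same absent segment is filled in: the patient's "baseline segment score will be carried forward (BOCF) to impute the Week 104 segment score when calculating the total SES-CD score".

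SAP 4.1.3.1 refers to this handling before it lists either analysis: "The handling of patients with partially available segments is detailed in Section" 4.1.3, and "this is not considered as true missing data". Two analyses follow.

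- Analysis 1 (Non-Responder): patients still in the study but "missing endoscopy scores (i.e., the assessment was not done) will be imputed as non-responders within the analysis". Evaluable patients who withdrew are also failures, apart from withdrawals on or after 15 February 2022.
- Analysis 2 (As Observed): "If a patient has missing data at a visit, they will be removed from the analysis and no imputation will be performed".

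The general definition of As Observed in SAP 4.1.3 is: "Within this analysis only the available data at each visit will be summarized. No imputation will be performed for missing data or treatment withdrawals".

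**The concern.** As Observed should show the result in patients who were actually assessed. Because an absent segment is declared not to be missing data, the removal rule in Analysis 2 does not reach a partly scored patient. That patient stays in the denominator as a failure, while a patient with no endoscopy leaves it. The more complete record gets the worse treatment.

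Only two binary analyses are planned for endoscopic improvement and remission, and both contain the rule. Agreement between them says nothing about the effect of incomplete endoscopies, and nothing else in the plan would reveal it.

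**Working it through.** **Tracing the rules.** There is no stated figure to reproduce: the SAP plans no tests and no sample size calculation.

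| Patient at Week 108 | Analysis 1 | As Observed |
|---|---|---|
| All baseline-scored segments scored | Classified on scores | Classified on scores |
| One baseline-scored segment unscored | Failure | Failure |
| No endoscopy, evaluable | Failure | Removed |

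**Same patient, two endpoints.** Take disease confined to ileum and right colon, both scoring 0 at Week 108, with the rectum unscored but 0 at baseline. The continuous derivation gives a total of 0. That meets the SES-CD threshold in SAP 1.3.3 (at most 4, or 2 for ileal patients, with no subcategory score above 1). The binary derivation gives failure.

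**Direction.** The rule only ever assigns failure, so it can turn a responder into a failure and never the reverse. For the SAP 1.3.3 threshold, an unscored segment can only add to the total and cannot lower the highest subscore. A patient whose scored segments already fail is therefore a true failure, and only patients whose scored segments pass can be misclassified.

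**Formulas.** Let F be the number fully scored, P the number partly scored, and M the evaluable patients without a Week 108 endoscopy who are counted as failures in Analysis 1. Let r be the response rate in F and q the true response rate in P.

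- Analysis 1 under the rule: rF/(F+P+M). With P correctly scored: (rF+qP)/(F+P+M). Loss: qP/(F+P+M).
- As Observed under the rule: rF/(F+P). With P correctly scored: (rF+qP)/(F+P). Loss: qP/(F+P).
- The Analysis 1 loss is (F+P)/(F+P+M) times the As Observed loss, so it is smaller whenever M is above 0 and the loss is not zero.

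**Illustration.** None of these inputs is in the documents. Assume F+P+M = 100, M = 40 and r = q = 40%.

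| P | F | Analysis 1: rule / scored | Loss (points) | As Observed: rule / scored | Loss (points) |
|---|---|---|---|---|---|
| 5 | 55 | 22/100 = 22.0% / 24.0% | 2.0 | 22/60 = 36.7% / 40.0% | 3.3 |
| 10 | 50 | 20/100 = 20.0% / 24.0% | 4.0 | 20/60 = 33.3% / 40.0% | 6.7 |
| 20 | 40 | 16/100 = 16.0% / 24.0% | 8.0 | 16/60 = 26.7% / 40.0% | 13.3 |

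At P = 10 with q = 20%, the losses are 2/100 = 2.0 points and 2/60 = 3.3 points. With q = 0 both are zero.

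**Net error.** Keep P = 10 and q = 40%, and let m be the true response rate among the 40 patients without endoscopy. The rate over all 100 is (20+4+40m)/100: 24% at m = 0 and 40% at m = 40%. As Observed under the rule reports 33.3%, so its net error runs from +9.3 to -6.7 points.

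**The case against.** The best defence is that the SAP does not contradict itself. It excludes imputation for missing data and withdrawals, says an absent segment is neither, and prespecifies how the endpoint is then derived. The endpoint also has a reason to demand every segment: a requirement that no segment exceeds a subscore of 1 cannot be confirmed when one was not seen.

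Part of this stands. The rule is prespecified and is reasonable in Analysis 1. But the same bullet says the absent segment will be imputed for the continuous score, so the SAP itself treats it as unobserved. And a criterion that cannot be confirmed leaves the patient unclassified. In an analysis limited to available data, that points to removal and not to failure.

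The limits on importance also stand. The SES-CD threshold endpoint is exploratory (SAP 1.3.3), the continuous score does not use the failure rule, the study is single-arm and descriptive, and the report is synoptic with limited efficacy data (SAP 4). The SAP nowhere presents As Observed as a check on segment handling.

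A reader might infer that both analyses understate the response rate overall, and by the same amount. The documents do not support either. As Observed also drops withdrawals and patients without endoscopy, which can push its rate up. The two losses have different denominators. Where an impassable narrowing blocked access, it scores 3 (Protocol Appendix 11) and already fails the SAP 1.3.3 threshold, so for that endpoint the rule costs nothing in such patients.

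**Conclusion.** The concern holds in a limited form. In As Observed, counting a patient as a failure because a baseline-scored segment is unscored at Week 108 conflicts with that analysis's own definition, and neither planned binary analysis can show the rule's effect. The effect is zero or downward: qP/(F+P) in As Observed and the smaller qP/(F+P+M) in Non-Responder.

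Its size cannot be computed from the documents. The illustrated 3.3 to 13.3 points (As Observed) and 2.0 to 8.0 points (Non-Responder) rest on assumed counts and on partly scored patients responding as often as fully scored ones. With q = 0 the effect vanishes. It is one component of bias, and the net bias of either analysis is not established here.

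**What to change.** - In SAP 4.1.3.1, state that the segment failure rule applies to Analysis 1 only.
- In Analysis 2, remove patients with a baseline-scored segment unscored at Week 108, as patients with no endoscopy are removed.
- Add a separately labelled sensitivity analysis that classifies these patients from the carried-forward segment scores already derived for the continuous endpoint. It should not sit inside As Observed, because carrying a score forward is itself imputation.
- Report how many patients the rule affects in each analysis.
- Correct the carry-forward sentence, which names Week 104 although the endoscopy is at Week 108.

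The cost is SAP wording, one derived flag and one extra summary. As Observed loses a few patients, some of whom may be failures on their scored segments. In the example with P = 10 and q = 0, removal gives 20/50 = 40.0% where full scoring would give 20/60 = 33.3%. The sensitivity analysis is therefore needed alongside removal. Its own weakness is that it could miss new disease in an unscored segment that was unaffected at baseline.

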4.1 GENERAL CONSIDERATIONS

4.1.1 Analysis of Study Conduct

The number of patients who discontinued early (early discontinuation of OLE treatment or early termination from the study) or completed the study will be tabulated.

Reasons for early discontinuation of treatment or early termination from the study will be listed and summarized. Any eligibility criteria exceptions and other major protocol deviations will also be summarized.

Since Part 1 (OLE) of GA29145 was terminated by the Sponsor on 15th February 2022, no patients are expected to reach treatment completion. As a result of this, the end of Part 1 (OLE) of GA29145 is defined from the last dose date in GA29145 on 15th May 2022.

In summary, the following will be summarised for GA29145 Part 1 (OLE):

- Analysis populations
- Patient disposition
- Study treatment completion/discontinuation
- Study completion/discontinuation
- Major protocol deviations
- Exposure

Treatment Labels

For the OLE population, the only treatment arm to be summarized is:

Group	Patients Included
OLE Etrolizumab	Patients in the OLE population who receive at least one dose of etrolizumab in Study GA29145 Part 1 (OLE)

All tables should be presented by treatment group only.

Part 1 (OLE) Day 1

OLE Study Day 1 is defined as the day patient has the first receipt of study drug in GA29145 Part 1 (OLE).

Baseline

Baseline is defined as the last available assessment prior to first receipt of study drug in the Induction Phase of the parent study, GA29144.

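### SAP 4.1.3.1 exempts every study-drug withdrawal on or after 15 February 2022 from non-responder status, whereas 4.1.3 and 4.1.3.3 exempt only sponsor-termination withdrawals after that date

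*SAP*

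**What the plan says.** Three places in the SAP set the exception to counting withdrawals as failures.

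- **SAP 4.1.3 (Maximum Hypothetical Evaluable Visit).** The scope is explicit: "For the hybrid LOCF analysis and non-responder analyses, this will impute patients who have withdrawn as a non-responder until the 15th May 2022". The exception follows: "This excludes patients who withdrew from study drug with reason being stated as" termination of the study by the sponsor, after 15 February 2022. For those patients, "these patients will not be imputed as non-responders and will be considered" treatment completers, with their data entering as observed.
- **SAP 4.1.3.3 (CDAI and clinical remission, hybrid LOCF).** It repeats the same reason and the same date.
- **SAP 4.1.3.1 (endoscopic improvement and remission, Analysis 1 - Non-Responder).** Withdrawals who could have reached Week 108 are failures under a composite strategy. The exception then reads: "This excludes patients who withdrew from study drug on or after 15th February 2022". No reason is required, and 15 February itself is included.

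SAP 4.1.1 fixes the date of the sponsor's action: "Since Part 1 (OLE) of GA29145 was terminated by the Sponsor on 15th February 2022". SAP 4.4, on changes to planned analyses, deals only with anti-therapeutic antibodies and gives no ground for a separate endoscopy rule.

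**The concern.** A composite strategy counts stopping for lack of efficacy or for an adverse event as treatment failure. A carve-out for patients stopped by the sponsor is sensible, because that stop says nothing about the drug. SAP 4.1.3.1 as worded goes further and removes every withdrawal in the window, including those the composite is meant to capture.

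The same withdrawal can then be a failure for remission and exempt for endoscopy at the same Week 108 visit. Two programmers working from different sections could flag the same patient differently. Endoscopic improvement is one of the two efficacy summaries that SAP 4.1.3 names.

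**Working it through.** The plan gives no figure to reproduce here. The check compares the rules and then uses date arithmetic to find who can be affected.

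**1. The rules side by side**

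| Section | Analysis | Reason required | Date |
|---|---|---|---|
| SAP 4.1.3 | Hybrid LOCF and non-responder | Study terminated by sponsor | After 15 Feb 2022 |
| SAP 4.1.3.3 | Remission, hybrid LOCF | Study terminated by sponsor | After 15 Feb 2022 |
| SAP 4.1.3.1 | Endoscopy, non-responder | None | On or after 15 Feb 2022 |

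SAP 4.1.3 names the non-responder analyses, so it and 4.1.3.1 govern the same analysis and disagree. The missing-endoscopy rule in 4.1.3.1 does not bring an exempt patient back as a failure, because it covers only patients who remain in the study.

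**2. Who can be affected by the missing reason condition**

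Inputs: 15 February 2022 (SAP 4.1.1), 15 May 2022 (SAP 4.1.3, end of evaluability), and Week 108 = 108 × 7 = 756 days after Day 1. Visit windows are ignored.

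- Evaluable at Week 108: Day 1 no later than 15 May 2022 − 756 days = 19 April 2020.
- Week 108 still ahead on 15 February 2022: Day 1 after 15 February 2022 − 756 days = 21 January 2020.
- Width of this enrolment band: 89 days. The ±7-day visit window would widen it to 14 January to 26 April 2020.

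**3. A worked case (hypothetical patient)**

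- Day 1 on 1 March 2020. Week 108 falls due on 27 March 2022.
- Maximum hypothetical study day = 15 May 2022 − 1 March 2020 = 805, which is at least 756, so the patient is evaluable.
- The patient stops for lack of efficacy on 10 March 2022 and has no usable Week 108 endoscopy.
- CDAI and clinical remission at Week 108 (4.1.3.3): failure.
- Endoscopic improvement and remission at Week 108: failure under 4.1.3, exempt under 4.1.3.1.

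**4. Direction**

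With N evaluable patients, r responders and m such withdrawals, 4.1.3 gives r/N. If 4.1.3.1 drops the m patients, the rate is r/(N − m), which is never below r/N. SAP 4.1.3.1 does not itself say that they are dropped.

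**5. Likely size, under assumptions**

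The documents give no enrolment or withdrawal dates. I assume uniform OLE entry from a start date up to 19 April 2020 and a constant rate L per year of withdrawal for reasons other than sponsor termination, with no competing sponsor stops.

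Affected share = f × mean of exp(−L(2.07 − t)) × (1 − exp(−L·t)), for t uniform on 0 to 89/365.25 years. Here t is the time from 15 February 2022 to the patient's Week 108 date, 2.07 years is 756 days, and f is the fraction of evaluable patients whose Day 1 lies in the 89-day band.

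| Assumed start of OLE entry | f | L = 0.1 | L = 0.3 | L = 0.6 |
|---|---|---|---|---|
| 1 Jul 2015 | 89/1754 = 5.1% | 0.051% | 0.102% | 0.113% |
| 1 Jul 2016 | 89/1388 = 6.4% | 0.064% | 0.129% | 0.142% |
| 1 Jan 2018 | 89/839 = 10.6% | 0.106% | 0.214% | 0.235% |

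Per 600 evaluable patients (also assumed) that is 0.30 to 1.41 patients. If they are dropped, an assumed 40% rate becomes 40/(1 − share) = 40.02% to 40.09%.

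**6. The date boundary**

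A sponsor stop recorded on 15 February 2022 is exempt under 4.1.3.1 but a failure under 4.1.3 and 4.1.3.3. The number of such stops is unknown and may be zero.

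**The case against.** The strongest defence is that 4.1.3.1 is shorthand for the rule just set out in 4.1.3. That is plausible, but 4.1.3.1 does not say so. Its references back to 4.1.3 concern partially available segments and evaluability, not this exemption. The conflict stands.

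Other objections carry weight and limit the point:

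- **The worked case assumes no usable endoscopy.** Protocol 4.4.4.4 calls for an ileocolonoscopy at early withdrawal if that comes before Week 108. Appendix 1 allows the withdrawal visit up to 30 days after the last dose, and 4.4.4.4 allows the procedure up to 10 days after the visit. A stop on 10 March 2022 could therefore yield an examination close to 27 March. The analysis text in SAP 4.1.3.1 does not say how such an examination maps to Week 108, so the case is possible but need not be typical.
- **The size rests on assumed inputs.** Two of them push it up: withdrawal for other reasons continues unchanged after the termination announcement, and exempt patients leave the denominator.
- **The stakes are low.** The study has no tests or comparisons (SAP 2.1), the SES-CD threshold endpoint is exploratory (SAP 1.3.3), the report is synoptic (SAP 4), and Analysis 2 of the same endpoint imputes nothing for withdrawals.

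A reader might also infer that sponsor-terminated patients have no rule of their own, and that the general bullets in 4.1.3 would bring them back as failures ("Evaluable patients with missing data will be set as a non-responder") or by carrying values forward ("For evaluable patients with missing data, Last Observation Carried Forward (LOCF) will be used from their most recent available data"). The documents do not support this. SAP 4.1.3 states for both analyses that these patients enter as observed, and the missing-data rules in 4.1.3.1 and 4.1.3.3 cover only patients still in the study.

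**Conclusion.** The inconsistency is certain on the text; its effect is small and possibly nil. SAP 4.1.3.1 lacks the reason condition that 4.1.3 and 4.1.3.3 share, and it uses a different date boundary. No rationale is given for either difference.

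The missing reason condition can affect only patients who entered the OLE between about 21 January and 19 April 2020 and who withdrew for another reason before Week 108 without a usable Week 108 endoscopy. The estimate of roughly none to one patient depends on the assumed entry dates, withdrawal rates and 600 evaluable patients. The upward direction holds only if exempt patients leave the denominator.

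A reader might infer that the endoscopic results, or their subgroup splits, are materially inflated, or that the wider exemption was chosen to favour endoscopy. The documents support neither. They give no counts, the plausible overall shift is under 0.1 percentage point from an assumed 40%, and nothing indicates intent. This is a minor wording correction.

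**What to change.** - In SAP 4.1.3.1, Analysis 1, limit the exemption to withdrawals whose recorded reason is termination of the study by the sponsor. Keep all other withdrawals in the window as non-responders if they could have reached Week 108.
- Say there, by reference to 4.1.3, that exempt patients enter as observed.
- Use one date boundary in 4.1.3, 4.1.3.1 and 4.1.3.3. Including 15 February 2022 fits the termination date in SAP 4.1.1.

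The cost is one revised sentence in 4.1.3.1, a matching date in the other two sections and one shared derivation flag. No new data or analysis is needed. It is best settled before the Part 1 database snapshot.
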